| MedDRA | Medical Dictionary for Regulatory Activities |
| OC | Observed Case |
| OPDC | Otsuka Pharmaceutical Development and Commercialization, Inc. |
| CCI | Otoaka i narmaccaticai Development and Commercianzation, me. |
| PE | Physical examination |
| CCI | Thysical examination |
| PT | Preferred Term |
| QTc | Corrected QT interval |
| QTcF | QT interval as corrected for heart rate by Fridericia's formula |
| QTcN | QT interval as corrected for heart rate by the FDA Neuropharm Division |
| SAE | Serious adverse event |
| SAS | Simpson Angus Scale |
| SAS® | Statistical Analysis System® |
| SAP | Statistical Analysis Plan |
| SBP | Systolic blood pressure |
| SOC | System Organ Class |
| | J 6 |

| Abbreviation | Definition |
|---------------------|----------------------------------|
| TEAE | Treatment-emergent adverse event |
| TSH | Thyroid stimulating hormone |
| ULN | Upper limit of normal |
| WHO | World Health Organization |

1 Introduction

This statistical analysis plan (SAP) expands the statistical section of the protocol 331-201-00191 (version 6.0) and documents in detail the statistical methodologies and data analysis algorithms and conventions to be applied to the analysis and reporting of the safety and tolerability data collected in the study. All amendments to the protocol have been taken into consideration in developing this SAP.

2 Study Objectives

Primary: To assess the long-term safety and tolerability of brexpiprazole monotherapy in children and adolescents of 5 to 17 years old with irritability associated with autism spectrum disorder (ASD).

Secondary: To assess the long-term efficacy of brexpiprazole monotherapy in the same patient population.

3 Trial Details

3.1 Study Design

This is a phase 3, multicenter, single-arm, open-label extension trial designed to assess the long-term safety and tolerability of oral brexpiprazole monotherapy in children and adolescents with irritability associated with ASD. Enrollment into the trial will be drawn from eligible subjects who complete the double-blind treatment period of the phase 3 ASD trial (Trial 331-201-00148¹), and in the investigator's judgment, could potentially benefit from continued investigational treatment with oral brexpiprazole.

The trial is planned to be conducted on an outpatient basis. Individual subjects' participation into the trial will be up to 29 weeks, including 26 weeks of open-label treatment, and 3 weeks of follow-up period. See Figure 3.1-1 for the design schematic of the trial. The trial will be organized as follows.

Screening Phase: Subjects who completed the double-blind treatment period of Trial 331-201-00148 (also referred to as the parent trial) and are deemed compliant with the protocol will be screened for eligibility at the last assessment visit of the double-blind treatment period. A separate fully executed informed consent/assent will be obtained for this open-label extension trial (Trial 331-201-00191²) before any procedures specific to this trial are performed. Unless specified otherwise, the assessments at the last visit in the double-blind treatment period of the parent trial will serve as the baseline measures for this open-label extension trial. Medical history will be updated for this trial, if necessary.

Open-label Treatment Phase: Eligible subjects will receive 26 weeks of daily treatment with brexpiprazole in Trial 331-201-00191. Subject will start the open-label dosing of brexpiprazole - the investigational medicinal product (IMP) on the very next day of the last assessment visit of the double-blind treatment period in the parent trial. Subjects will be evaluated at baseline and all the scheduled visits which will occur at the end of Weeks 1, 2, 3, 4, 8, 14, 18, 22 and 26 during the treatment period. Visits are to occur within ± 2 days of the target visit date. All required evaluations as described in the Schedule of Assessments (see Table 3.7-1of the Protocol for Trial 331-201-00191) will be performed. If a subject discontinues from the trial before the end-of-trial visit at Week 26, assessments or procedures noted for the Week 26 visit must be completed at an early termination (ET) visit. Attempts should be made to complete all evaluations prior to the administration of any new medications or treatment. Of note, the baseline, Week 2, Week 14, and Week 26 visits will occur in the clinic. All other visits will be virtual or in clinic. Where the investigator and caregiver make the decision to conduct a visit virtually, the visit will be conducted by means of telecommunications technology.

Follow-up Phase: Subjects will have a follow-up contact 21 (\pm 2) days after the last dose of the IMP to assess any new or ongoing AEs and to record any concomitant medications. The follow-up contact also applies to the subjects who are prematurely withdrawn from the trial.

[figure not shown]

Figure 3.1-1 Trial Design Schematic

3.2 Trial Treatments

The first dose of open-label brexpiprazole will be taken the following day after the last dose of double-blind IMP is taken in the parent trial so that treatment continues without interruption. Whenever possible, it is anticipated that the last dose of IMP in the double blind, phase 3 efficacy trial will be taken on the day of the baseline visit for the open-label trial. Subjects should not be dosed using double-blind and open-label IMP on the same day. Throughout 26 weeks of treatment in this open-label extension trial, enrolled subjects will follow a titration/dosing schedule depending upon subject's body weight at the baseline visit. Subjects will receive a target dose range of 1 to 1.5 mg/day if body weight < 50 kg, and 1.5 to 3 mg/day if \geq 50 kg. Refer to Table 3.2-1 of the Protocol for Trial 331-201-00191, which shows the titration/dosing schedule per subject's body weight stratum at baseline.

4 Sample Size and Power Justification

The sample size planned for this open-label extension trial is not based on considerations of statistical power.

Participants in this trial will be the subjects who completed the double-blind treatment period of the parent trial (Trial 331-201-00148) and who would likely benefit from a longer term of treatment with brexpiprazole in the judgement of the investigator. The sample size for this rollover trial will not exceed that of the parent trial (ie, 119 randomized subjects).

5 Data Sets for Analysis and Missing Data

5.1 Data Sets for Analysis

To adequately describe the statistical analyses and reporting, three analysis populations are defined as follows.

- Enrolled Sample: Consists of subjects who completed the double-blind treatment period of the parent trial and who gave consent/assent for participation into this open-label trial and who also met all the eligibility criteria for this trial.
- Safety Sample: Consists of all Enrolled subjects who took at least one dose of the IMP as indicated on the dosing records of this open-label extension trial. A subject will be excluded from this population only if there is documented evidence that the subject has not taken the IMP (ie, number of tablets/capsules dispensed = number of tablets/capsules returned, or no IMP dispensed). If a subject is dispensed trial medications but subsequently lost to follow-up, the subject will be considered exposed to the IMP.

• Efficacy Sample: All subjects in the Safety Sample who have a baseline assessment and at least one post-baseline assessment of the Aberrant Behavior Checklist - Irritability (ABC-I) subscale score.

Summary statistics of demographics, baseline characteristics and subject disposition variables will be computed on the Enrolled Sample. Summary statistics of adverse events and all other safety parameters will be computed on the Safety Sample, and summary statistics of all efficacy parameters will be computed on the Efficacy Sample.

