#### 3.13 Protocol Deviations

This trial is intended to be conducted as described in this protocol. In the event of a significant deviation from the protocol due to an emergency, accident, or mistake (eg, violation of informed consent/assent process, IMP dispensing or subject dosing error, treatment assignment error, subject enrolled in violation of eligibility criteria or concomitant medication criteria), the investigator or designee will contact the sponsor at

the earliest possible time by telephone. The investigator and sponsor will come as quickly as possible to a joint decision regarding the subject's continuation in the trial. This decision will be documented by the investigator and the sponsor, and reviewed by the site monitor.

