#### 7.2 Datasets for Analysis

The following analysis samples are defined for this trial:

Enrolled Sample: All subjects who sign an ICF/IAF for the trial and are enrolled into the trial. Safety Sample: All subjects who receive at least 1 dose of brexpiprazole.

Efficacy Sample: All subjects in the Safety Sample who have a baseline assessment and at least one post-baseline assessment of the ABC-I subscale score.\_

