## 1 Trial 331-201-00191 COVID-19 Protocol Summary

#### 1.1 Trial Design Schematic

[figure not shown]

Figure 1.1-1 COVID-19 Impact Trial Design Schematic - Subjects Who Rollover Directly From Trial 331-201-00148

Note: In order to be eligible for this trial, the baseline visit must be in office per the protocol. Eligible subjects are those subjects who complete Trial 331-201-00148. Subjects who were not able to rollover directly into this trial (Trial 331-201-00191) or are terminated early from Trial 331-201-00148 due to the COVID-19 pandemic will have an opportunity to enter this trial upon completion of in office screening and baseline visits as detailed in Figure 1.1-2.

[figure not shown]

Figure 1.1-2 Trial Design Schematic - Delayed Rollover Subjects From Trial 331-201-00148

Note: In order to eligible for this trial, the screening and baseline visits must be in office.

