## 3 Trial Population

#### 3.1 Inclusion Criteria

There are no changes to the inclusion criteria due to COVID-19 for purposes of this addendum. For delayed rollover subjects, inclusion criteria can be found in Section 3.4.2 of the protocol.

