#### 3.2 Exclusion Criteria

There are no changes to exclusion criteria for subjects who rollover directly from Trial 331-201-00148.

Delayed rollover subjects (ie, those who were unable to directly rollover from Trial 331-201-00148 due to the COVID 19 pandemic or who were terminated early due to the COVID-19 pandemic) will be excluded if they meet any of the exclusion criteria presented in Table 3.2-1.

Tab	Die 3.2-1 Exclusion Criteria for Delayed Rollover Subjects From Trial 331-201-00148
1.	Sexually active males or FOCBP who do not agree to practice 2 different methods of birth control or remain abstinent during the trial and for 30 days after the last dose of IMP. If employing birth control, 2 of the following precautions must be used: vaginal diaphragm, intrauterine device, birth control pill, birth control implant, birth control depot injection, condom with spermicide, or sponge with spermicide.
2.	Females who are breast-feeding and/or who have a positive pregnancy test result prior to receiving IMP.
3.	Subjects who have a significant risk of committing violent acts, serious self-harm, or suicide based on history or routine psychiatric status examination, or those who are homicidal or considered to be a high risk to others, or subjects with an answer of "yes" on C-SSRS Suicidal Ideation Item 4 (Active Suicidal Ideation with Some Intent to Act, Without Specific Plan) at entry or within the past three months, OR Subjects with a response of "yes" on the C-SSRS Suicidal Ideation Item 5 (Active Suicidal Ideation with Specific Plan and Intent) at entry or within the past three months, OR Subjects with a response of "yes" on any of the 5 C-SSRS Suicidal Behavior Items(actual attempt, interrupted attempt, aborted attempt, preparatory acts, or behavior) at entry or within the past year.
4.	Non-pharmacological therapy (eg, psychotherapy, behavior modification) is not stable for 30 days prior to screening and is not likely to be consistent throughout the trial.
5.	
 
Subjects with Type I or Type II diabetes are excluded if all of the following criteria are not met:
 
HbA1c ≤ 6.5%,
 
Screening fasting glucose is ≥ 70 mg/dL and ≤ 100 mg/dL or nonfasting glucose is ≥ 70 mg/dL and ≤ 139 mg/dL. If the nonfasting glucose is ≥ 139 mg/dL, subjects must be retested in the fasting state. At retest, fasting glucose must be ≤ 100 mg/dL
 

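### SAP 5.1 ties the Safety Sample to parent-trial completion and full eligibility, whereas protocol 7.2 includes every dosed subject

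*SAP*

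**What the plan says.** Protocol 7.2 sets one condition: "Safety Sample: All subjects who receive at least 1 dose of brexpiprazole". Its Enrolled Sample needs only a signed consent or assent form and enrolment.

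SAP 5.1 builds its sets in sequence. The Enrolled Sample holds subjects who completed the parent double-blind period, "who gave consent/assent for participation into this open-label trial and who also met all the eligibility criteria for this trial". The next set is then taken from it: "Safety Sample: Consists of all Enrolled subjects who took at least one dose of the IMP as indicated on the dosing records". The sentence after that reads "A subject will be excluded from this population only if there is documented evidence that the subject has not taken the IMP", and a subject who was dispensed drug and then lost to follow-up is counted as exposed. The Efficacy Sample is a subset of the Safety Sample.

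The SAP runs all safety analyses on the Safety Sample (sections 5.1 and 8), and disposition, reasons for discontinuation and protocol deviations on the Enrolled Sample (6.1 and 6.3). Section 6.3 lists departures from entry criteria among the deviation types to be summarized.

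**The concern.** Safety is the primary objective, so its analysis set should contain everyone exposed to open-label drug. A set that also depends on eligibility and parent-trial completion can lose exposed subjects, and the SAP gives no reason for being narrower than the protocol section it says it expands.

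The loss would be hard to notice. The proposed listings of deaths, SAEs and discontinuations for AEs (CT-9.1 to CT-9.3) are themselves confined to the Safety Sample. A subject withdrawn once an entry violation came to light would also be missing from the disposition and discontinuation tables. In addition, two programmers could build different primary-objective populations from the same paragraph.

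**Working it through.** **1. Definitions side by side**

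| Dosed subject | Protocol 7.2 | SAP 5.1, first sentence | SAP 5.1, next sentence taken alone |
|---|---|---|---|
| Completed parent trial, met all criteria | in | in | in |
| Breached an entry criterion | in | out | in |
| Did not complete parent trial | in | out | in |

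Protocol 3.9 defines a screen failure as someone who consented but did not start open-label treatment. A dosed entry violator is therefore not a screen failure under the protocol, and not Enrolled under the SAP.

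**2. Can such subjects exist?**

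- *Entry violators.* Protocol 3.13 names "subject enrolled in violation of eligibility criteria or concomitant medication criteria" as an example of a significant deviation and leaves continuation to a joint decision by investigator and sponsor. Protocol 3.7.1.1 lets eligibility rest on earlier laboratory values when last-visit results are pending and provides for action if exclusionary values arrive later; dosing starts the next day. (Section 3.7.3.2, by contrast, asks for results to be reviewed before drug is started.)
- *Non-completers.* COVID-19 Addendum 1.1 says subjects "terminated early from Trial 331-201-00148 due to the COVID-19 pandemic will have an opportunity to enter this trial". Addendum 3.2 counts among delayed rollovers those "who were terminated early due to the COVID-19 pandemic) will be excluded if they meet any of the exclusion criteria". Yet Addendum 3.1 says "There are no changes to the inclusion criteria due to COVID-19 for purposes of this addendum", and inclusion criterion 1 in protocol 3.4.2 requires completion of the parent trial. This group may be empty.

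**3. A check inside the SAP.** Section 6.3 tabulates entry-criteria deviations on a sample that, by its 5.1 definition, contains nobody who failed a criterion.

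**4. Size.** The documents give no count of affected subjects, so there is no plan figure to reproduce. The input n = 119 is the ceiling in SAP section 4 (subjects randomized in the parent trial). The number left out (k), the 10 events and the group size of 60 are assumptions.

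*Upper bound for an event never seen*, one-sided 95%, 1 − 0.05^(1/n):

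| k left out | n | Bound |
|---|---|---|
| 0 | 119 | 2.49% |
| 1 | 118 | 2.51% |
| 5 | 114 | 2.59% |
| 10 | 109 | 2.71% |

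*Incidence* with an assumed 10 of 119 (8.4%). The low end is (10 − k)/(119 − k), where every subject left out had the event. The high end is 10/(119 − k), where none did.

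| k | Low | High |
|---|---|---|
| 1 | 9/118 = 7.6% | 10/118 = 8.5% |
| 3 | 7/116 = 6.0% | 10/116 = 8.6% |
| 5 | 5/114 = 4.4% | 10/114 = 8.8% |

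If those left out had the event at the average rate, incidence stays at 8.4%.

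*Rare events.* A single SAE in one omitted subject goes from 1/119 = 0.84% to 0/118. SAP 8.1 also plans a table of TEAEs reaching 2% in either prior-treatment group. Two subjects meet that cut-off when 2/n ≥ 2%, so n ≤ 100. After one is lost, the other falls short when 1/(n − 1) < 2%, so n ≥ 52. With an assumed group of 60, 2/60 = 3.3% becomes 1/59 = 1.7%, and the term leaves that table.

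**The case against.** The strongest reply is that the intent is plain and the harmful reading unlikely. The SAP says it expands the protocol and announces no narrower population. It counts even dispensed-then-lost subjects as exposed, and 6.3 shows that its authors expect entry violators among the Enrolled. The sentence on non-intake may also apply only within the Enrolled, in which case SAP 5.1 does not contradict itself. This is fair evidence of intent, but it does not remove the written rule. The choice is between a Safety Sample that matches the protocol only by setting the first sentence aside, and one that is consistent within 5.1 but conflicts with protocol 7.2.

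Several narrower points stand:

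- The non-completer group adds little weight. SAP 7.1 does provide a baseline rule for subjects with a separate screening visit after the parent trial, but that fits completers who rolled over late, whom 5.1 admits.
- Some abnormal screening results are not violations, because protocol 3.7.3.2 allows enrolment with the medical monitor's permission.
- The 2% example needs a group of at least 52. If the two groups were equal (an assumption), that means 104 of 119, about 87%, rolling over. The full TEAE table (CT-8.2.2) has no cut-off, so a term that merely falls below 2% is still reported there. A sole event in an omitted subject is not.
- SAEs still reach the sponsor under protocol 5.3, and the deviation listing in SAP 6.3 carries no sample restriction. The gap is in the planned safety outputs, not in expedited reporting.
- Protocol 7.2 partly defines Enrolled by the word itself, so copying it without clarification would leave some room for doubt.

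**Conclusion.** The concern holds. SAP 5.1 as written conflicts with protocol 7.2 on the population for the primary objective, and it fits neither its own next sentence nor the deviation table in 6.3. The conclusion rests on the text and needs no assumption about numbers.

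The practical size is unknown and may be nil. Effects on precision are negligible; effects on incidence can go either way and are small unless the omitted subjects are enriched for events. The real exposure is the loss of a rare or single serious event from every safety table and listing. No direction of bias is established. It should be fixed, because it governs the main analysis set and correcting it costs almost nothing.

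**What to change.** In SAP 5.1:

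1. Define the Safety Sample as all subjects who took at least one dose of open-label IMP, whatever their eligibility or parent-trial completion. Keep the existing sentence that allows exclusion only on documented evidence of no intake.
2. Define the Enrolled Sample as in protocol 7.2 (signed consent or assent and enrolled). State that a later-discovered entry violation does not remove a subject, so that the tables in 6.1 and 6.3 can show such cases.

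Separately, reconcile COVID-19 Addendum 1.1, the footnote to its Table 1.2-1 and its section 3.2 with Addendum 3.1 and inclusion criterion 1 on whether subjects terminated early from the parent trial may enter. Which rule applies is for the sponsor to decide; the Safety Sample definition in item 1 works either way.

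The cost is two definitions in the SAP and one clarification in the addendum. No new data are needed.

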5.2 Handling of Missing Data

For scoring via the aggregation of component items of the efficacy and safety scales, and how to handle the items with unrecorded (missing) ratings for the scoring, refer to Section 11 for details.

The Observed Case (OC) dataset for the parameters (eg, efficacy or safety variables) of interest will consist of all the actual observations or assessments of the parameters recorded at the visits during the open-label treatment period and the follow-up period. Note that if observations or assessments are unrecorded, thus missing, at a visit, the missing values will not be imputed. Subjects discontinued from treatment before Week 26 will have an ET visit where all assessments originally scheduled for the Week 26 visit will be made. Such data collected at the ET visit (or any other unscheduled visits, if any) will be mapped to a specific visit per the visit window algorithm given in Section 10.3. In the instances where a subject discontinues the treatment early but somehow does not subsequently attend the ET visit, all scheduled assessments after the timepoint of his or her treatment discontinuation will remain missing. All by-visit analysis (including summary) will be based on the OC dataset.

The Last-Observation-Carried-Forward (LOCF) dataset include all OC data and in addition the imputed data per a commonly used imputation rule (the LOCF rule) as follows: If no observation or assessment is recorded at a scheduled visit, the missing value for that visit will be imputed by carrying forward the last available (ie, the immediately preceding) observation or assessment (inclusive of the value at an ET visit, if any). Note that baseline data cannot be carried forward to impute post-baseline values.

Of particular interest is the timepoint of the end-of-trial visit at Week 26. Serving as a kind of supplementary evidence for the results, the analysis will be repeated on the Week 26 LOCF data for each analysis performed on the Week 26 OC data.

6 Study Conduct

6.1 Subject Disposition, Completion Rate and Reasons for Discontinuation

Subject disposition will be summarized on the Enrolled Sample by clinical center as well as by prior treatment group. Subject completion rate and reasons for discontinuation will be summarized on the Enrolled Sample by prior treatment group. Subjects who are evaluated at the last scheduled visit of the open-label treatment period will be defined as trial completers. For purposes of this trial, subjects who complete the Week 26 visit will be defined as trial completers.

6.2 Treatment Compliance

Based on the IMP panel of the Case Report Form (CRF), an individual subject's overall compliance score with respect to his/her taking IMP will be calculated by dividing the number of tablets/capsules (actually) taken by the total number of tablets/capsules scheduled to be taken for the observed treatment period, then multiply by 100. For the subject who is prematurely discontinued from treatment or lost to follow-up, the last dose date recorded on the subject will be used as the endpoint of the observed treatment period. The denominator (ie, number of tablets/capsules scheduled to be taken) will be downwardly adjusted for early treatment discontinuation.

